12.6 Safety Conclusions

A notably larger percentage (≥ 5 percentage points) of udenafil-treated than placebo-treated subjects reported at least 1 TEAE (79.0% versus 67.5%) and at least 1 drug-related TEAE (66.0% versus 42.5%). The incidence of TEAEs of Grade ≥ 3 , serious TEAEs, drug-related serious TEAEs, and TEAEs resulting in temporary or permanent discontinuation of study drug was similar between treatment groups.

A notably greater percentage (≥ 5 percentage points) of subjects in the udenafil group as compared to the placebo group reported headache (39.0% versus 25.5%), flushing (14.5% versus 6.0%), epistaxis (10.0% versus 3.0%), nausea (9.5% versus 4.5%), and erection increased (6.3% of males versus 0.8% of males).

There were no clinically important differences in the TEAE profile among subgroups defined by gender (female, male), race (Caucasian/White, non-Caucasian/White), ethnicity (Hispanic or Latino/Latina, not Hispanic or Latino/Latina), age (tertiles at baseline), and weight (tertiles at baseline).

Severe TEAEs were reported for 10 (5.0%) udenafil-treated subjects and 6 (3.0%) placebo-treated subjects; no life-threatening TEAEs were reported in either treatment group. Dizziness was the only severe TEAE reported by > 1 subject (2 placebo subjects).

No subject died during the study. At least 1 serious TEAE was reported by 14 (7.0%) subjects in the udenafil group and 10 (5.0%) subjects in the placebo group. No individual serious TEAE was reported by > 2 subjects in either treatment group. Hospitalization was reported for 23 subjects (14 udenafil, 9 placebo) during the study. No transplants were reported.

At least 1 TEAE leading to temporary or permanent discontinuation of study drug was reported by 18 (9.0%) subjects in the udenafil group and 13 (6.5%) subjects in the placebo group. Headache was the only TEAE leading to temporary or permanent discontinuation of study drug reported by > 2 subjects in either treatment group (3 subjects each in the udenafil and placebo groups).

There were no clinically important treatment group differences for clinical laboratory findings and vital signs.

Overall, udenafil was safe and well tolerated in this study.

13 Discussion and Overall Conclusions

The primary aim of this study was to evaluate the effect of 26 weeks of treatment with udenafil on exercise capacity in adolescents with Fontan physiology. The protocol-specified primary exercise outcome was change in maximal VO_2 and secondary exercise outcomes included change in VO_2 at VAT, change in ventilatory efficiency at VAT, and work rate at VAT. All exercise measures demonstrated a favorable outcome for udenafil relative to placebo.

For maximal VO_2 , the udenafil group had a mean increase from baseline to Week 26 compared to a mean decrease in the placebo group (44.40 mL/min versus -3.65 mL/min; $p=0.071$). When standardized by each subject's body weight, the least squares mean treatment group difference was 0.64 mL/kg/min ($p=0.092$).

The following secondary efficacy endpoints measured at VAT also indicated greater exercise capacity in the udenafil group than the placebo group at Week 26:

- VO_2 at VAT: Mean increase (improvement) for udenafil as compared to a mean decrease in the placebo group (29.65 mL/min versus -8.01 mL/min; $p=0.023$). When standardized by each subject's body weight, the least squares mean treatment group difference was 0.78 mL/kg/min ($p=0.012$).
- VE/VCO_2 at VAT: Greater mean decrease (improvement) for udenafil as compared to placebo (-0.76 versus -0.05; $p=0.011$).
- Work rate at VAT: Greater mean increase (improvement) for udenafil as compared to placebo (3.46 watts versus 0.31 watts; $p=0.029$).

An additional efficacy aim evaluated the effect of 26 weeks of treatment with udenafil on the performance of a single ventricle. The primary measure of ventricular performance was change in MPI, which indicated improvement with udenafil versus placebo (-0.02 versus 0.01; $p=0.024$).

Common TEAEs with a notably greater incidence (≥ 5 percentage points) in the udenafil group as compared to the placebo group included headache, flushing, epistaxis, nausea, and erection increased (in males). These events have been reported with other PDE-5 inhibitors (Pfizer 2017).

There were no clinically important differences in the TEAE profile among subgroups defined by gender (female, male), race (Caucasian/White, non-Caucasian/White), ethnicity (Hispanic

or Latino/Latina, not Hispanic or Latino/Latina), age (tertiles at baseline), and weight (tertiles at baseline).

The incidence of TEAEs of Grade ≥ 3 , serious TEAEs, drug-related serious TEAEs, and TEAEs resulting in temporary or permanent discontinuation of study drug was similar between treatment groups. No subject died during the study. No individual serious TEAE was reported by > 2 subjects in either treatment group. Hospitalization was reported for 23 subjects (14 udenafil, 9 placebo) during the study.

There were no clinically important treatment group differences for clinical laboratory findings and vital signs. Overall, udenafil was safe and well tolerated in this study.

In summary, this study achieved its primary clinical objectives by demonstrating that udenafil administered orally at 87.5 mg BID for 26 weeks led to improved exercise capacity as compared to placebo in adolescents with Fontan physiology. In addition, myocardial performance was improved in the group treated with udenafil.

14 Tables, Figures and Graphs Referred to but not Included in the Text

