9.1 Overall Study Design and Plan Description

This was a Phase 3 randomized, placebo-controlled, double-blind, 26-week, multicenter study of the effects of udenafil versus placebo in adolescents with Fontan physiology. The target sample size was 400 adolescents (200 per treatment group).

At PHN sites, potential subjects were identified through a screening chart review. Subjects who met initial study eligibility criteria, were receiving primary cardiac care at the PHN site, and were geographically local to the PHN site were approached regarding participation. In

addition, auxiliary sites in the United States and Korea were recruited at the beginning of the study to augment the number of potential subjects.

Subjects who agreed to participate had baseline testing performed to determine eligibility with inclusion/exclusion criteria. Subjects performed an exercise test to maximal effort to be eligible for randomization and study drug initiation. A subject who was unable to achieve a maximal effort (respiratory exchange ratio [RER] ≥ 1.10) on exercise testing but who otherwise qualified for inclusion, was offered the opportunity to repeat the test within 2 weeks of time of consent. Subjects with maximal minute oxygen consumption (VO_2) $< 50\%$ of predicted for age and gender, based on their most recent prior clinical exercise test, were excluded from the study.

Eligible subjects were stratified by ventricular morphology (single left vs single right or mixed) and randomly assigned by a web-based system at the data coordinating center (DCC) to 1 of 2 treatment groups: orally administered udenafil (87.5 mg BID) or matching placebo BID. The first dose of randomized study drug was administered at the clinic (Visit 1, baseline).

Approximately 2 hours (± 30 minutes) post dosing, resting heart rate and blood pressure were measured, and the subject performed a self-limited 6-minute walk. A repeat heart rate and blood pressure were measured immediately following and approximately 2 hours (± 30 minutes) following the 6-minute walk. Subjects who had a drop in systolic blood pressure > 20 mmHg from the pre- to post-6-minute walk measurement, or had a drop in systolic blood pressure below the 5th percentile for age, were excluded from receiving any further study drug. Continuing subjects were dispensed their initial supply of study medication and instructed to take 1 tablet orally BID.

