12.2 Adverse Events (AEs)

12.2.1 Brief Summary of Adverse Events

A notably larger percentage (≥ 5 percentage points) of udenafil-treated than placebo-treated subjects reported at least 1 TEAE (79.0% versus 67.5%) and drug-related TEAE (66.0% versus 42.5%). The incidence of TEAEs of Grade ≥ 3 , serious TEAEs, drug-related serious TEAEs, and TEAEs resulting in temporary discontinuation (identified as drug interrupted in listings) or permanent discontinuation of study drug was similar between treatment groups ([Table 24](#)).

Table 24: Overall Summary of Treatment-emergent Adverse Events (Safety Population)

Subjects with ≥ 1 :	Udenafil (N=200) n (%)	Placebo (N=200) n (%)
TEAE	158 (79.0)	135 (67.5)
Drug-related TEAE	132 (66.0)	85 (42.5)
TEAEs of Grade ≥ 3	10 (5.0)	6 (3.0)
Serious TEAEs	14 (7.0)	10 (5.0)
Drug-related serious TEAEs	4 (2.0)	2 (1.0)
TEAE that led to temporary or permanent discontinuation of study drug	18 (9.0)	13 (6.5)

TEAE=treatment-emergent adverse event

Source: [Table 14.3.2](#)Program: [t_14_3_2.sas](#)

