12.3.1.2 Other Serious Adverse Events

At least 1 serious TEAE was reported by 14 (7.0%) subjects in the udenafil group and 10 (5.0%) subjects in the placebo group ([Table 32](#)). Serious TEAEs reported by at least 2 subjects included chest pain (2 udenafil subjects), influenza (2 udenafil subjects), syncope (2 placebo subjects) and dyspnoea (1 udenafil subject and 1 placebo subject). All other serious TEAEs were reported by a single subject each.

Hospitalization was reported for 23 subjects (14 udenafil, 9 placebo) during the study ([Table 14.3.18](#)). Hospitalized subjects are identified in [Listing 16.2.7.3](#). No transplants were reported during the study ([Table 14.3.18](#)). Tabular summaries of transplants and hospitalizations by weight tertile are provided in [Table 14.3.19A](#), [Table 14.3.19B](#), and [Table 14.3.19C](#). Tabular summaries of transplants and hospitalizations by age tertile are provided in [Table 14.3.20A](#), [Table 14.3.20B](#), and [Table 14.3.20C](#).

Table 32: Serious Treatment-emergent Adverse Events Reported for ≥2 Subjects (Safety Population)

System Organ Class Preferred Term	Udenafil (N=200) n (%)	Placebo (N=200) n (%)
Subjects with ≥1 serious TEAE	14 (7.0)	10 (5.0)
General disorders and administration site conditions	2 (1.0)	1 (0.5)
Chest pain	2 (1.0)	0
Infections and infestations	2 (1.0)	3 (1.5)
Influenza	2 (1.0)	0
Nervous system disorders	2 (1.0)	5 (2.5)
Syncope	0	2 (1.0)
Respiratory, thoracic and mediastinal disorders	3 (1.5)	1 (0.5)
Dyspnoea	1 (0.5)	1 (0.5)

TEAE=treatment-emergent adverse event

Source: [Table 14.3.10](#)Program: [14_3_ae_tables.sas](#)

Six subjects (4 udenafil, 2 placebo) had serious TEAEs that were considered related to study drug ([Table 14.3.11A](#)). In the udenafil group, drug-related serious TEAEs included anxiety and bronchospasm reported in 1 subject and diplegia, retinal vascular occlusion, and palpitations reported in 1 subject each. In the placebo group, 2 subjects experienced a drug-related serious TEAE of syncope. Serious adverse events considered not related to study drug by the Investigator are summarized in [Table 14.3.11B](#). All serious TEAEs are listed in [Table 33](#).

A short description is provided below for each drug-related serious TEAE.

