6.5 Safety Evaluations

Safety assessments will be summarized for the Safety Population. No formal hypothesis testing will be performed.

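### Four categories of more serious adverse events are called similar between arms with no interval or margin, although the counts exclude neither no difference nor a doubling

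*Protocol*

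**What the plan says.** The document filed as the protocol is, from its Section 5 on, the clinical study report of the 26-week placebo-controlled trial. Its synopsis describes the separate open-label extension and is not used here.

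Section 12.2.1 first reports gaps that reach 5 percentage points: a larger share "of udenafil-treated than placebo-treated subjects reported at least 1 TEAE (79.0% versus 67.5%) and drug-related TEAE (66.0% versus 42.5"%). The next sentence, repeated in 12.6 and again in 13, covers Grade 3 or higher TEAEs together with the others: "serious TEAEs, drug-related serious TEAEs, and TEAEs resulting in temporary or permanent discontinuation of study drug was similar between treatment groups". Section 12.6 ends: "Overall, udenafil was safe and well tolerated in this study".

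The supporting figures are counts and percentages in Table 24 and the text. For example, "At least 1 serious TEAE was reported by 14 (7.0%) subjects in the udenafil group and 10 (5.0%) subjects in the placebo group" and, in 12.3.1.2, "Six subjects (4 udenafil, 2 placebo) had serious TEAEs that were considered related to study drug". Hospitalization is given separately: "Hospitalization was reported for 23 subjects (14 udenafil, 9 placebo) during the study".

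A gap of at least 5 points is defined as notable in 12.2.3, the subgroup section, and is also used in 12.2.1, 12.2.2, 12.2.2.2 and 12.6. It does not appear in the SAP. On safety, SAP 6.5 says: "No formal hypothesis testing will be performed". No safety margin or safety power is stated. The sample-size sections (report 9.7.2, SAP 3.0) concern maximal VO₂ only.

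**The concern.** *Similar* is a comparative verdict, and a reader will take it to mean that a material difference has been made unlikely. Counts this small cannot do that. The 5-point flag does not fill the gap, because it is an absolute cutoff. It is reasonable for headache (placebo 25.5%), but much less so for events seen in 1% to 6.5% of placebo subjects, where the rate must multiply before the flag responds.

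At stake is what a prescriber or regulator takes from the only placebo-controlled safety comparison in these documents. Failure to see a difference may be read as evidence that there is none.

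**Working it through.** **Inputs.** Udenafil v placebo, 200 subjects each (Tables 7 and 24): Grade 3 or higher 10 v 6; serious 14 v 10; drug-related serious 4 v 2; TEAEs leading to temporary or permanent discontinuation of study drug 18 v 13. Hospitalization 14 v 9 (12.3.1.2).

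**The report's own figures.** The percentages reproduce: 14/200 = 7.0%, 10/200 = 5.0%, 4/200 = 2.0%, 2/200 = 1.0%, 10/200 = 5.0%, 6/200 = 3.0%, 18/200 = 9.0%, 13/200 = 6.5%. There is no reported interval to reproduce.

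**Intervals.** For differences I used Newcombe's method. With Wilson limits l and u for each arm (1 = udenafil, 2 = placebo) and d = p1 − p2:
- lower limit = d − √[(p1 − l1)² + (u2 − p2)²]
- upper limit = d + √[(u1 − p1)² + (p2 − l2)²]

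For serious TEAEs the Wilson limits are 4.22% to 11.41% on udenafil and 2.74% to 8.96% on placebo, so:
- lower = 2.0 − √(2.78² + 3.96²) = −2.8
- upper = 2.0 + √(4.41² + 2.26²) = 7.0

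For ratios, the standard error of ln(RR) is √(1/a − 1/200 + 1/b − 1/200). For serious TEAEs this is √(1/14 + 1/10 − 2/200) = 0.402, so the limits are 1.40 × exp(±1.96 × 0.402) = 0.64 to 3.08.

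| Category | Counts | Difference, points (95% CI) | Risk ratio (95% CI) | Rise that equals 5 points |
|---|---|---|---|---|
| Grade 3 or higher | 10 v 6 | +2.0 (−2.1 to 6.3) | 1.67 (0.62 to 4.50) | 3.0% to 8.0%, 2.7-fold |
| Serious | 14 v 10 | +2.0 (−2.8 to 7.0) | 1.40 (0.64 to 3.08) | 5.0% to 10.0%, 2-fold |
| Drug-related serious | 4 v 2 | +1.0 (−1.8 to 4.1) | 2.0 (0.37 to 10.8) | 1.0% to 6.0%, 6-fold |
| Discontinuation of drug | 18 v 13 | +2.5 (−2.9 to 8.0) | 1.38 (0.70 to 2.75) | 6.5% to 11.5%, 1.8-fold |
| Hospitalization | 14 v 9 | +2.5 (−2.2 to 7.4) | 1.56 (0.69 to 3.51) | 4.5% to 9.5%, 2.1-fold |

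Every interval includes no difference, and every ratio interval includes 2. Of the four categories called similar, three do not exclude a 5-point excess. Drug-related serious TEAEs do exclude it (upper limit 4.1), but their observed ratio is already 2.

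**Chance of missing a doubling of serious TEAEs.** Assume a true placebo rate of 5% (the observed rate) and 10% on udenafil, with 200 per arm and a two-sided 0.05 test.
- Normal approximation: the pooled rate is 0.075, the null SE is √(2 × 0.075 × 0.925/200) = 0.0263 and the alternative SE is √(0.05 × 0.95/200 + 0.10 × 0.90/200) = 0.0262. Power = Φ[(0.05 − 1.96 × 0.0263)/0.0262] = Φ(−0.06) = 47.5%.
- Exact binomial enumeration of the pooled z test: power 47.2%, so 53% missed. With Fisher's test, power is 40.6%, so 59% missed.
- Exact chance that the observed gap reaches 5 points (10 subjects): 53.5%, so 46% missed.

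The result depends on the base rate. For true placebo rates of 3%, 4%, 6% and 7%, approximate power against a doubling is 30%, 39%, 55% and 63%.

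The 5-point flag performs unevenly. It picks up a doubling of drug-related serious TEAEs (1% to 2%) 0.2% of the time, but a doubling of discontinuation TEAEs (6.5% to 13%) 72% of the time.

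**The case against.** **The safety analysis was descriptive by design, so the absence of tests and margins follows the plan.** This stands: there is no departure from the SAP. But ruling out hypothesis tests does not rule out intervals. The report already gives least-squares differences with standard errors for laboratory values (Table 39), and p-values for vital signs that 12.5 describes as statistically significant (Table 41).

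**The report does not hide the numbers.** This also stands. Section 12.6 says that TEAEs and drug-related TEAEs were more frequent on udenafil, and prints 14 v 10 and the hospitalization counts. It makes no formal claim of equivalence.

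**The power figure is for a test that nobody planned.** Fair. It only illustrates what 200 per arm can show, and it takes the observed placebo rate as true. The intervals carry the argument.

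**Three stronger readings are tempting, and the documents do not support them.**
- A reader might infer that *similar* and *safe* were concluded because no gap reached 5 points. For *similar*, this is only an inference from adjacent sentences. For *safe*, it does not fit: the report reaches that conclusion despite gaps of 11.5 points (79.0% v 67.5%) and 23.5 points (66.0% v 42.5%). It also cites no deaths, no transplants, no life-threatening TEAEs, no single serious TEAE in more than 2 subjects per arm, and laboratory and vital-sign findings. Nor is it true in every subgroup that serious TEAE gaps stayed below 5 points. Table 38 shows 7/75 v 1/59 in the low weight tertile (9.3% v 1.7%, 7.6 points) and 6/72 v 2/61 in the low age tertile (8.3% v 3.3%, 5.05 points). These are small exploratory cells.
- A reader might think hospitalization was called similar. The available text only gives its counts.
- A reader might count several concordant signals of harm. Drug-related serious TEAEs are a subset of serious TEAEs, and inpatient hospitalization is itself a seriousness criterion (9.5.1.2.1), so these are largely one observation repeated.

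**Conclusion.** The point holds as one about unsupported comparative wording. For Grade 3 or higher, serious, drug-related serious and discontinuation TEAEs, the data are compatible with no difference and with at least a doubling. For serious TEAEs they range from a 36% reduction (ratio 0.64) to about a threefold increase (3.08), or up to about 7 points. That does not justify an unqualified statement of similarity. It does not demonstrate harm either, and no breach of the SAP is alleged.

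The intervals rest only on the reported counts and 200 per arm. The statement that a doubling of serious TEAEs is missed about half the time (53% by a two-sided 0.05 test, 46% by a 5-point rule) also assumes a true placebo rate of 5%. The end-of-text safety tables were not available. Their titles indicate counts and percentages; if they do contain intervals, those need only be brought into the text.

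**What to change.** 1. Add to Table 24, for every row, the udenafil-minus-placebo difference and the risk ratio, each with a 95% CI. Table 24 has no hospitalization row, so give the same figures where the 14 v 9 counts are reported.

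2. In 12.2.1, 12.6 and 13, replace *similar* for all four categories, including Grade 3 or higher and discontinuation TEAEs. For example: *numerically more frequent on udenafil; the intervals include no difference and do not exclude a doubling*.

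3. Follow the concluding statement on safety and tolerability with: *the study was not large enough to exclude an increase in serious TEAEs of up to about 7 percentage points (ratio up to about 3)*.

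No new data or tests are needed. The cost is extra columns in one table, an interval for hospitalization, a few reworded sentences and a slightly less favourable safety statement.

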12.2.2.2 Treatment-emergent Adverse Events Related to Study Drug

Drug-related TEAEs reported by $\geq 5\%$ of subjects in the udenafil group ([Table 14.3.7A](#)) included headache (38.0%), flushing (14.5%), epistaxis (7.5%), dizziness (6.5%), nausea (6.5%), erection increased (6.3% of males), and spontaneous penile erection (6.3% of males). Drug-related TEAEs reported by $\geq 5\%$ of subjects in the placebo group included headache (22.0%), dizziness (7.0%), and flushing (6.0%). A notably greater percentage (≥ 5 percentage points) of subjects in the udenafil group as compared to the placebo group reported drug-related headache (38.0% versus 22.0%), flushing (14.5% versus 6.0%), erection increased (6.3% of males versus 0.8% of males), spontaneous penile erection (6.3% of males versus 0.8% of males), and epistaxis (7.5% versus 1.5%).

Common drug-related TEAEs (reported by $\geq 2\%$ of all subjects) are summarized in [Table 26](#). TEAEs considered not related to study drug by the Investigator are summarized in [Table 14.3.7B](#).

Table 26: Most Common (≥2% of All Subjects) Treatment-emergent Adverse Events Related to Study Drug (Safety Population)

System Organ Class Preferred Term:	Udenafil (N=200) n (%)	Placebo (N=200) n (%)
Subjects with ≥1 TEAE related to study drug	132 (66.0)	85 (42.5)
Gastrointestinal disorders	30 (15.0)	19 (9.5)
Abdominal pain upper	6 (3.0)	6 (3.0)
Nausea	13 (6.5)	7 (3.5)
General disorders and administration site conditions	19 (9.5)	15 (7.5)
Chest pain	3 (1.5)	6 (3.0)
Fatigue	5 (2.5)	7 (3.5)
Infections and infestations	14 (7.0)	7 (3.5)
Upper respiratory tract infection	7 (3.5)	3 (1.5)
Nervous system disorders	89 (44.5)	55 (27.5)
Dizziness	13 (6.5)	14 (7.0)
Headache	76 (38.0)	44 (22.0)
Migraine	5 (2.5)	4 (2.0)
Reproductive system and breast disorders	15 (7.5)	3 (1.5)
Erection increased ^a	7 (6.3)	1 (0.8)
Spontaneous penile erection ^a	7 (6.3)	1 (0.8)
Respiratory, thoracic and mediastinal disorders	27 (13.5)	13 (6.5)
Epistaxis	15 (7.5)	3 (1.5)
Nasal congestion	5 (2.5)	4 (2.0)
Vascular disorders	31 (15.5)	13 (6.5)
Flushing	29 (14.5)	12 (6.0)

TEAE=treatment-emergent adverse event

a Percentage calculated based on number of male subjects in each treatment group.

Source: [Table 14.3.7A](#)

Program: [14_3_ae_tables.sas](#)

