Preferred Term:	Male Subjects (N=239)			Female Subjects (N=161)		
	Udenafil (N=111) n (%)	Placebo (N=128) n (%)	Total (N=239) n (%)	Udenafil (N=89) n (%)	Placebo (N=72) n (%)	Total (N=161) n (%)
Nausea	12 (10.8)	3 (2.3)	15 (6.3)	7 (7.9)	6 (8.3)	13 (8.1)
Vomiting	10 (9.0)	4 (3.1)	14 (5.9)	5 (5.6)	2 (2.8)	7 (4.3)
Chest pain	3 (2.7)	13 (10.2)	16 (6.7)	7 (7.9)	5 (6.9)	12 (7.5)
Nasopharyngitis	13 (11.7)	8 (6.3)	21 (8.8)	7 (7.9)	5 (6.9)	12 (7.5)
Upper respiratory tract infection	7 (6.3)	8 (6.3)	15 (6.3)	7 (7.9)	9 (12.5)	16 (9.9)
Dizziness	10 (9.0)	8 (6.3)	18 (7.5)	7 (7.9)	10 (13.9)	17 (10.6)
Headache	42 (37.8)	32 (25.0)	74 (31.0)	36 (40.4)	19 (26.4)	55 (34.2)
Epistaxis	11 (9.9)	1 (0.8)	12 (5.0)	9 (10.1)	5 (6.9)	14 (8.7)
Flushing	14 (12.6)	5 (3.9)	19 (7.9)	15 (16.9)	7 (9.7)	22 (13.7)

Source: [Table 14.3.4A](#) and [Table 14.3.4B](#)

Program: [14_3_ae_tables.sas](#)

Table 28: Most Common (≥5% of All Subjects) Treatment-emergent Adverse Events by Race Category (Safety Population)

Preferred Term:	Caucasian/White Subjects (N=324)			Non-Caucasian/White Subjects (N=65)		
	Udenafil (N=169) n (%)	Placebo (N=155) n (%)	Total (N=324) n (%)	Udenafil (N=29) n (%)	Placebo (N=36) n (%)	Total (N=65) n (%)
Nausea	14 (8.3)	6 (3.9)	20 (6.2)	4 (13.8)	2 (5.6)	6 (9.2)
Vomiting	11 (6.5)	4 (2.6)	15 (4.6)	3 (10.3)	0	3 (4.6)
Chest pain	8 (4.7)	14 (9.0)	22 (6.8)	2 (6.9)	2 (5.6)	4 (6.2)
Nasopharyngitis	15 (8.9)	10 (6.5)	25 (7.7)	5 (17.2)	3 (8.3)	8 (12.3)
Upper respiratory tract infection	13 (7.7)	17 (11.0)	30 (9.3)	1 (3.4)	0	1 (1.5)
Dizziness	16 (9.5)	12 (7.7)	28 (8.6)	1 (3.4)	3 (8.3)	4 (6.2)
Headache	64 (37.9)	42 (27.1)	106 (32.7)	13 (44.8)	6 (16.7)	19 (29.2)
Epistaxis	16 (9.5)	5 (3.2)	21 (6.5)	4 (13.8)	1 (2.8)	5 (7.7)
Flushing	25 (14.8)	11 (7.1)	36 (11.1)	4 (13.8)	1 (2.8)	5 (7.7)

Note: Summary excludes 11 subjects of unknown or not reported race.

Source: [Table 14.3.4C](#) and [Table 14.3.4D](#)

Program: [14_3_ae_tables.sas](#)

Table 29: Most Common (≥5% of All Subjects) Treatment-emergent Adverse Events by Ethnicity Category (Safety Population)

Preferred Term:	Hispanic or Latino/Latina Subjects (N=56)			Not Hispanic or Latino/Latina Subjects (N=342)		
	Udenafil (N=31) n (%)	Placebo (N=25) n (%)	Total (N=56) n (%)	Udenafil (N=168) n (%)	Placebo (N=174) n (%)	Total (N=342) n (%)
Nausea	4 (12.9)	1 (4.0)	5 (8.9)	15 (8.9)	8 (4.6)	23 (6.7)
Vomiting	4 (12.9)	3 (12.0)	7 (12.5)	11 (6.5)	3 (1.7)	14 (4.1)
Chest pain	1 (3.2)	6 (24.0)	7 (12.5)	9 (5.4)	12 (6.9)	21 (6.1)

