An adverse event cluster including occurrences of hypotension (e.g., blood pressure decreased, blood pressure diastolic decreased, blood pressure systolic decreased, hypotension, procedural hypotension), loss of consciousness, dizziness (e.g., dizziness, dizziness exertional, procedural dizziness), presyncope, or syncope (syncope, syncope vasovagal) will be summarized as follows:

- The number and percent of subjects reporting at least 1 TEAE from the above cluster will be summarized by treatment group.
- The number and percent of patients reporting each of the preferred terms will also be summarized by treatment group.
- The 2 summaries will also be repeated by
 - age tertiles
 - weight tertiles.

An adverse event cluster including death, hospitalization for heart failure, and transplant will be summarized as follows:

- The number and percent of subjects reporting at least 1 TEAE from the above cluster will be summarized by treatment group.
- The number and percent of patients reporting each of the preferred terms will also be summarized by treatment group.
- The 2 summaries will also be repeated by
 - age tertiles
 - weight tertiles.

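### The safety conclusions cite one of two erection terms, at 6.3% of udenafil males; the report's own tertile figures put either event at 8.1% to 12.6%

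*Protocol*

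**What the plan says.** The closing list in section 12.6 covers treatment-emergent events of any cause and uses a threshold of 5 percentage points. Its only erection entry is "and erection increased (6.3% of males versus 0.8% of males". Section 13 repeats the list without figures: "headache, flushing, epistaxis, nausea, and erection increased (in males".

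The body of the report says more. Section 12.2.2 gives 6.3% of udenafil males for each of two terms, *erection increased* and *spontaneous penile erection*, but its list of notable differences keeps only the first. Section 12.2.2.2, on drug-related events, puts both above the threshold: "erection increased (6.3% of males versus 0.8% of males), spontaneous penile erection (6.3% of males versus 0.8% of males". Table 26 shows 7 v 1 males for each, with the footnote "Percentage calculated based on number of male subjects in each treatment group". Section 12.2.3 reports both terms by age and weight tertile, although its paragraph on gender names only the first.

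SAP section 6.5.2 plans tables by system organ class and preferred term and sex-specific denominators for sex-specific events. It also plans a few clusters of related terms, for example "dizziness (e.g., dizziness, dizziness exertional, procedural dizziness". No cluster is planned for erection events.

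**The concern.** The two terms are near-synonyms, and each has the same count on udenafil. The notable-difference rule works one preferred term at a time, and the conclusions carry only one of the two. Someone who reads only 12.6 or 13 meets a single figure of 6.3% and would take it as the frequency of this kind of event in adolescent boys. That would be right only if the same 7 boys reported both terms. If they were partly different boys, the conclusions understate how often a male-specific effect occurred. At stake is the accuracy of one incidence figure in a safety summary; no efficacy test depends on it.

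**Working it through.** **Inputs.**
- Male denominators, Table 27: "Udenafil (N=111) n" and "Placebo (N=128) n".
- Drug-related counts, Table 26: 7 v 1 for each term.
- Any-cause rate on udenafil, section 12.2.2: 6.3% of males for each term.
- Weight tertiles, section 12.2.3, udenafil males (*erection increased*; *spontaneous penile erection*): low 5.0% and 10.0%; high 5.6% and 8.3%. The medium tertile is not given.
- Udenafil tertile sizes, both sexes, Table 31: 75, 68 and 57, which sum to 200.

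**1. Reproduce the stated figure.** 7/111 = 6.3% and 1/128 = 0.8%. No other whole number gives 6.3% of 111 (6/111 = 5.4%, 8/111 = 7.2%). So each term has 7 udenafil males both for any cause and for drug-related events. Drug-related events are a subset of all events, so on udenafil the two sets hold the same males.

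**2. Upper bound.** With no overlap, 7 + 7 = 14 males and 14/111 = 12.6%. This is compatible with the 15 udenafil subjects in the drug-related row for reproductive system and breast disorders, where the SAP counts each subject once.

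**3. Lower bound.** Find whole numbers that reproduce the tertile percentages, with at most 7 males per term.
- High tertile: 5.6% and 8.3% fit only 36 males, with 2 and 3 events.
- Low tertile: 5.0% and 10.0% fit 20 males (1 and 2), 40 males (2 and 4) or 60 males (3 and 6). Sixty is impossible, since 6 + 3 = 9 exceeds the total of 7.
- Medium tertile, by subtraction from 111 males and 7 events per term:
  - low = 40: 35 males with 7 − 2 − 2 = 3 and 7 − 4 − 3 = 0;
  - low = 20: 55 males with 7 − 1 − 2 = 4 and 7 − 2 − 3 = 2.

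A male lies in one tertile only, so overlap within a tertile cannot exceed the smaller of its two counts.
- low = 40: overlap at most 2 + 0 + 2 = 4, so at least 14 − 4 = 10 males (10/111 = 9.0%).
- low = 20: overlap at most 1 + 2 + 2 = 5, so at least 14 − 5 = 9 males (9/111 = 8.1%).

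Either way, 7 distinct males is excluded.

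**4. Placebo, drug-related.** 1 male with each term means 1 to 2 distinct males: 1/128 = 0.8% to 2/128 = 1.6%.

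**5. Risk difference, drug-related.** SE = √[p₁(1−p₁)/111 + p₂(1−p₂)/128], with limits at ±1.96 SE.
- 9 v 2: 8.1% − 1.6% = 6.5 points. SE = √(0.0811×0.9189/111 + 0.0156×0.9844/128) = 2.8 points; 95% CI 1.0 to 12.1.
- 14 v 2: 12.6% − 1.6% = 11.1 points before rounding of the two rates. SE = √(0.1261×0.8739/111 + 0.0156×0.9844/128) = 3.3 points; 95% CI 4.5 to 17.6.

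These are large-sample intervals on small counts and should be read as approximate.

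**6. The 5-point rule for the second term, any cause.** The overall placebo count for *spontaneous penile erection* from any cause is not shown. With 1 male the difference is 6.31 − 0.78 = 5.5 points. With 2 it is 6.31 − 1.56 = 4.7 points.

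**The case against.** The defence is substantial. The sentence in 12.6 is true as written: it names one preferred term and gives that term's rate. The second term is not concealed, since 12.2.2, 12.2.2.2, 12.2.3 and Table 26 all report it, the percentages being over male denominators. Reporting by preferred term is what the SAP prescribes, and having no cluster for these terms is not a departure from it. The SAP was final on 23 June 2016 and the blind was broken on 19 July 2019, so any grouping now is post hoc. All of this stands.

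A reader might infer that leaving the second term out of 12.6 breaks the report's own 5-point rule. The documents do not show that. The list in 12.6 is for any cause, and the placebo count needed is missing. A second placebo male with an event judged unrelated would explain why the term is notable among drug-related events but not in the any-cause list. In that case the omission follows the rule, and it is the split into two terms that keeps the second one out.

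A reader might also fault the organ-class row for dividing by all 200 subjects. That class is not confined to males, so its denominator is appropriate. It simply cannot serve as the combined male rate.

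None of this answers the remaining point: the conclusions give no figure for males with either event, and the single-term 6.3% cannot be that figure.

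**Conclusion.** The concern holds as a minor point about completeness. Between 9 and 14 of 111 udenafil males (8.1% to 12.6%) had at least one of the two events, where the conclusions show 6.3%. The drug-related placebo rate is 0.8% to 1.6%. Even at 9 v 2, the smallest contrast within these bounds, the combined drug-related difference of 6.5 points passes the report's own 5-point threshold.

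The lower bound assumes that the tertile percentages use male denominators and cover the same events as section 12.2.2. Treating the two terms as one kind of event is a judgement from their wording; the documents do not say so.

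Some stronger readings are not supported. A reader might take 12.6% as the true rate, or say that the conclusions understate it by half. Both need zero overlap, which is a ceiling and not an estimate; at 9 males the shortfall is 2 of 9, about a fifth. A reader might also rank the combined effect with or above flushing (12.6%), nausea (10.8%) and epistaxis (9.9%) in males. At 8.1% to 9.0% it lies below all three. The extension synopsis gives no erection figure, so nothing there needs correcting. No test, analysis population or overall safety conclusion changes.

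**What to change.** Add one grouped row, *erection increased or spontaneous penile erection*, labelled post hoc. Count each male once, use male denominators, show both arms, and give the risk difference with its 95% CI. Do this for events of any cause and for drug-related events. Take the exact number of distinct males from the adverse event listing by subject (Listing 16.2.7.1); that replaces the range above and also settles the any-cause placebo count. Cite the row in sections 12.2.2, 12.6 and 13 beside the preferred-term figures, which stay as they are.

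The grouping follows the SAP's practice for dizziness, syncope and hypotension and its rule on sex-specific denominators. The cost is one row from data already held. The downside is a less favourable adverse event figure, chosen after the data were seen and therefore to be presented as descriptive.
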